6.4. Study Intervention Compliance

When participants are dosed at the site, they will receive study intervention directly from the investigator or designee, under medical supervision. The date and time of each dose administered in the clinic will be recorded in the source documents. The dose of study intervention and study participant identification will be confirmed at the time of dosing by a member of the study site staff other than the person administering the study intervention.

Participants may self-inject PegIFN during specified visits in the PegIFN treatment phase (see [Table 4](#)) as allowed per country requirements. Site staff will telephone to confirm the dose as described above.

6.5. Dose Modification

Dose modifications of GSK3228836 are not planned for this study. Dose modifications of PegIFN are allowed per [Section 7.2](#).

6.6. Study Intervention after the End of the Study

No intervention is planned at the end of the study, although participants may be asked to enrol in a long-term roll-over study based on their response.

6.7. Treatment of Overdose

For this study, any dose of GSK3228836 greater than 300 mg within a 24-hour time period will be considered an overdose.

GSK does not recommend specific treatment for an overdose.

In the event of an overdose, the investigator should:

- Contact the Medical Monitor immediately.
- Closely monitor the participant for AE/SAE and laboratory abnormalities until GSK3228836 can no longer be detected systemically (at least 105 days).
- Obtain a plasma sample for PK analysis within 1 day from the date of the last dose of study intervention if requested by the Medical Monitor (determined on a case-by-case basis).

- Document the quantity of the excess dose as well as the duration of the overdosing in the case report form (CRF).

Decisions regarding dose interruptions or dose modifications of PegIFN will be made by the investigator in consultation with the Medical Monitor based on the clinical evaluation of the participant.

6.8. Concomitant Therapy

Any medication or vaccine (including over-the-counter or prescription medicines, vitamins, and/or herbal supplements or other specific categories of interest) that the participant is receiving at the time of enrollment or receives during the study must be recorded along with:

- reason for use
- dates of administration including start and end dates
- dosage information including dose and frequency

The Medical Monitor should be contacted if there are any questions regarding concomitant or prior therapy.

Concomitant medications, including NA therapy, should be recorded.

Traditional Chinese medicine (TCM) and/or acupuncture as it relates to CHB therapy should be avoided during the duration of the study. If participants report use of TCM and/or acupuncture, then details must be recorded in the concomitant medication CRF.

6.8.1. Nucleos(t)ide Treatment during and after the End of the Study

The investigator is responsible for ensuring that consideration has been given to the care of the participant's medical condition, and that participants are able to continue their therapy over the duration of the study.

The investigator is responsible for ensuring that consideration has been given to the post-study care of the participant's medical condition, whether or not GSK is providing specific post-study treatment.

6.8.2. Prohibited Medications and Non-Drug Therapies

The following concomitant medications for GSK3228836 are not permitted during the study:

- Immunosuppressing drug (e.g., prednisone) use >2 weeks duration from 3 months prior to Screening through the final Follow-up visit (see Section 5.2), unless required for safety
- Prior treatment with any oligonucleotide or small interfering RNA (siRNA) within 12 months prior to the first dosing
- Creatine-containing gym supplements
- Anticoagulation therapy
- Anti-platelet therapy

Refer to the local label for prohibited concomitant medications for PegIFN [[Pegasys](#), 2017]. Telbivudine is contraindicated in the PegIFN label; the combination of telbivudine with interferon products (such as peginterferon) to treat hepatitis may increase the risk of peripheral neuropathy [[Tyzeka](#), 2013].

7. DISCONTINUATION OF STUDY INTERVENTION AND PARTICIPANT DISCONTINUATION/WITHDRAWAL

A participant may withdraw from the study treatment at any time at his/her own request or may be withdrawn at any time at the discretion of the Investigator for safety, behavioural or administrative reasons. In rare instances, it may be necessary for a participant to permanently discontinue (definitive discontinuation) study intervention. Participants that withdraw from treatment for any reason should be encouraged to complete all their on-treatment and follow-up visits and assessments. Every effort should be made to complete the early termination (ET) study procedures and observations if the participant does not enter post-treatment follow-up.

Any laboratory parameter that meets the stopping criteria should be repeated to confirm the value prior to withdrawal.

For participants meeting the stopping criteria (Section 7.1- Section 7.2), participants should be monitored until laboratory abnormalities resolve, stabilise, or return to within baseline values as indicated. The participant must then attend the visits specified in the SoA. See the SoA for data to be collected at the time of discontinuation of study intervention and follow-up and for any further evaluations that need to be completed.

7.1. GSK3228836 Dose Modification and Stopping Criteria

7.1.1. GSK3228836 Liver Chemistry Stopping Criteria

Liver chemistry stopping, and increased monitoring criteria have been designed to assure participant safety and to evaluate liver event etiology. Study intervention will be discontinued for a participant if the liver stopping criteria are met. Restart/re-challenge guidelines are presented in Section 10.6 ([Appendix 6](#)).

Discontinuation of study intervention for abnormal liver tests is required when:

- a participant meets one of the conditions outlined in [Table 9](#).
- when in the presence of abnormal liver chemistries not meeting protocol-specified stopping rules, the investigator believes study intervention discontinuation is in the best interest of the participant.

[Table 9](#) lists the criteria for withholding or discontinuing the study medication in a study participant with elevation of ALT. Additional testing will be performed (see safety follow-up procedures for participants who meet increased monitoring or stopping criteria), and the participant monitored until liver chemistry abnormalities resolve, stabilise, or return to within baseline values. The participant must then attend the follow-up visits specified in the SoA.

Every attempt must be made to have the participant evaluated (within 24 hours) for repeat assessment of liver chemistries and additional testing and close monitoring (a specialist or hepatology consultation is recommended). Participants must be monitored weekly until liver chemistry abnormalities (ALT, AST, alkaline phosphatase, bilirubin) resolve, stabilise, or return to within baseline values. Upon completion of the safety follow-up procedures (see below), the participant must attend the follow-up visits specified in the SoA.

Table 9 GSK3228836 Liver Chemistry Monitoring and Stopping Criteria

ALT Level	Monitoring Plan	Discontinuation
10 x ULN \leq ALT < 12 x ULN and Bilirubin \leq 1.5 x ULN and INR \leq 1.5 (if available)	Monitor twice weekly Additional lab assessments	Permanently discontinue IMP if ALT > 10 x ULN > 4 weeks
ALT \geq 12 x ULN and Bilirubin \leq 1.5 x ULN and INR \leq 1.5 (if available)	Hold dose Monitor twice weekly Additional lab assessments if not already done Take off hold: GSK3228836 150 mg SC weekly when ALT < 10 x ULN; increasing dose to 300 mg (if applicable) should be agreed with Medical Monitor	Permanently discontinue IMP if any of the following apply: 
 • ALT \geq 10 x ULN > 4 weeks • ALT \geq 12 x ULN recurs after IMP taken off hold
ALT \geq 3 x ULN and 1.5 x ULN < bilirubin \leq 2 x ULN (>35% direct) and INR \leq 1.5 (if available)	Hold dose Monitor twice weekly Additional lab assessments if not already done Take off hold: GSK3228836 150 mg SC weekly when bilirubin returns to < 1.5 x ULN; increasing dose to 300 mg (if applicable) should be agreed with Medical Monitor	Permanently discontinue IMP if the following recurs after IMP taken off hold: 1.5 x ULN < bilirubin \leq 2 x ULN (>35% direct) And INR \leq 1.5 (if available)
ALT \geq 3 x ULN and any of the following apply: 
 • bilirubin > 2 x ULN (>35% direct) • associated with the appearance or worsening of hepatitis symptoms • INR > 1.5 (if available) 		Permanently discontinue IMP Monitor twice weekly until stable ALT Additional lab assessments if not already done

ALT = alanine aminotransferase; IMP = investigational medicinal product; ULN = upper limit of normal

***Notes:**

- Any abnormal laboratory parameters that meet the criteria for individual treatment discontinuation must be confirmed by retest of a new collection of blood samples as soon as possible.
- Deterioration considered clinically significant from the baseline in the liver parameters must be confirmed by retesting ALT, total bilirubin, direct bilirubin and INR (if available).
- If one criterion in the list above is met and confirmed by retesting, further treatment may be discontinued for this participant after discussion with the Medical Monitor. Results of retesting must be evaluated before the next dose is administered.
- Monitor participant until liver chemistry abnormalities resolve, stabilise, or return to within baseline values.
- Cases such as Gilbert syndrome, where baseline bilirubin values are high, should be discussed with the Medical Monitor, to assess if it is a case of DILI or the participant may continue with dosing.

The procedures listed below are to be followed if a participant meets any of the liver chemistry stopping criteria defined in [Table 9](#):

Notify the Medical Monitor within 24 hours of learning of the abnormality to confirm the participant's study treatment cessation and follow-up.

Complete the Liver Event CRF.

Complete the "Safety Follow-up Procedures" listed below.

Safety Follow-up Procedures for Participants Who Meet Any of The Liver Monitoring and Stopping Criteria:

Viral hepatitis serology including:

- Hepatitis A IgM antibody;
 - Cytomegalovirus IgM antibody;
 - Epstein-Barr viral capsid antigen IgM antibody (or if unavailable, obtain heterophile antibody or monospot testing);
 - Hepatitis E IgM antibody.
 - Hepatitis B virus DNA load
 - Hepatitis C virus RNA load
 - Hepatitis D virus antibody
- Obtain a blood sample for pharmacokinetic (PK) analysis as soon as possible following the occurrence of an event. Record the date/time of the PK blood sample collection and the date/time of the last dose of study treatment prior to blood sample collection on the CRF. If the date or time of the last dose is unclear, provide the participant's best approximation. Instructions for sample handling and shipping are included in the SRM.

- Serum creatine phosphokinase (CPK) and lactate dehydrogenase (LDH).
- Review fractionated bilirubin
- Assess eosinophilia
- Record the appearance or worsening of clinical symptoms of hepatitis (fatigue, nausea, vomiting, right upper quadrant pain or tenderness, fever, rash or eosinophilia) as relevant on the Adverse Event (AE) CRF.
- Record use of concomitant medications, acetaminophen, herbal remedies, other over the counter medications, or putative hepatotoxins on the Concomitant Medications CRF.
- Record alcohol use on the Liver Events CRF.

The following are **required for participants who meet the ALT and bilirubin stopping criteria** but are optional for other abnormal liver chemistries.

- Anti-nuclear antibody, anti-smooth muscle antibody, Type 1 anti-liver kidney microsomal antibodies and quantitative total immunoglobulin G (IgG or gamma globulins).
- Serum acetaminophen adduct high performance liquid chromatography (HPLC) assay (quantifies potential acetaminophen contribution to liver injury in participants with definite or likely acetaminophen use in the preceding week [James, 2009]), if available.
- Liver imaging (ultrasound, magnetic resonance, or computerised tomography) or Liver biopsy to evaluate liver disease.
- The Liver Imaging and/or Liver Biopsy CRFs are also to be completed if these tests are performed.

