 - There is new cANCA or pANCA positivity

Treatment Hold/Treatment Discontinuation

- Hold study treatment during evaluation of alternative causes for decreased C3 and/or C4 associated with increased inflammatory markers including one or more of hs-CRP, MCP-1, Bb and C5a
- Discontinue study treatment permanently if persistent change from baseline (≥ 4 weeks) in biomarker pattern (decreased C3/C4 associated with increased inflammatory markers including one or more of hs-CRP, MCP-1, Bb, C5a) without clear alternative explanation.
- Discontinue study treatment permanently if suspect clinical sequelae of complement activation, DIVI, vasculitis or autoimmunity regardless of biomarkers changes or persistence.

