10.5. Appendix 5: Genetics

USE/ANALYSIS OF DNA

- Genetic variation may impact a participant's response to study intervention, susceptibility, severity and progression of disease. Variable response to study intervention may be due to genetic determinants that impact drug absorption, distribution, metabolism, and excretion; mechanism of action of the drug; disease etiology; and/or molecular subtype of the disease being treated. Therefore, where local regulations and IRB/IEC allow, a blood sample will be collected for DNA analysis.
- DNA samples will be used for research related to GSK3228836 or chronic hepatitis B and related diseases. They may also be used to develop tests/assays (including diagnostic tests) related to GSK3228836 or other 2'-MOE ASOs, and CHB. Genetic research may consist of the analysis of one or more candidate genes or the analysis of genetic markers throughout the genome or analysis of the entire genome (as appropriate).
- Additional analyses may be conducted if it is hypothesised that this may help further understand the clinical data.
- The samples may be analysed as part of a multi-study assessment of genetic factors involved in the response to GSK3228836 or study interventions of this class. The results of genetic analyses may be reported in the clinical study report or in a separate study summary.
- The sponsor will store the DNA samples in a secure storage space with adequate measures to protect confidentiality.
- The samples will be retained while research on GSK3228836 (or study interventions of this class) or chronic hepatitis B continues but no longer than 15 years after the last participant last visit or other period as per local requirements.

10.6. Appendix 6: Liver Safety: Required Actions and Follow-up Assessments and Study Intervention Restart Guidelines

Phase 2 liver chemistry stopping and increased monitoring criteria have been designed to assure participant safety and evaluate liver event etiology.

The procedures listed below are to be followed if a participant meets any of the liver chemistry stopping criteria defined in Section 7.1.

If criteria for permanent discontinuation of IP are met, immediately withdraw the participant from study treatment.

Notify the Medical Monitor within 24 hours of learning of the abnormality to confirm the participant's study treatment cessation and follow-up.

Complete the Liver Event CRF.

Complete the "Safety Follow-up Procedures" listed below.

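### Protocol Section 7.1.1 gives two answers on permanent liver stops: the text, Table 9 and Appendix 6 require the stop, but a note under Table 9 makes it optional after confirmation

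*Protocol*

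**What the plan says.** Several places in the protocol make the stop mandatory.

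- Section 7.1.1, opening text: "Study intervention will be discontinued for a participant if the liver stopping criteria are met".
- Section 7.1.1, next paragraph: "Discontinuation of study intervention for abnormal liver tests is required when" a participant meets one of the Table 9 conditions.
- Table 9, Discontinuation column: an imperative in all four rows. In rows 1 to 3 it depends on persistence or recurrence. In row 4 it applies at once: "Permanently discontinue IMP Monitor twice weekly until stable ALT".
- Appendix 6 (Section 10.6): "If criteria for permanent discontinuation of IP are met, immediately withdraw the participant from study treatment".
- The procedure below the Table 9 notes has the site notify the Medical Monitor within 24 hours to confirm the participant's "study treatment cessation and follow-up".

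Section 7 adds a confirmation step: "Any laboratory parameter that meets the stopping criteria should be repeated to confirm the value prior to withdrawal".

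The third note under Table 9 differs. If a criterion in the list is "met and confirmed by retesting, further treatment may be discontinued for this participant after discussion with the Medical Monitor". It then requires the retest to be evaluated before the next dose. The fifth note sends cases with high baseline bilirubin, such as Gilbert syndrome, to the Medical Monitor for a decision on continuing.

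**The concern.** A site that confirms a permanent-stop criterion finds one sentence telling it to stop and another leaving the stop to a discussion. Two things depend on the answer.

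The first is safety. Two of the row 4 triggers are ALT at or above 3 x ULN with bilirubin above 2 x ULN, and ALT at or above 3 x ULN with INR above 1.5. Note 3 to Table 17 (Appendix 2) describes these as possible Hy's Law. A stopping rule for that pattern should have one reading. The protocol expects ALT flares (Section 2.3.1) and gives the sponsor's belief that they are therapeutic (Section 4.2), so sites could use any discretion differently.

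The second is access to PegIFN. Under Section 5.3 a permanent liver stop bars PegIFN, whereas a hold or dose reduction leaves a route to it. Two participants with the same confirmed laboratory result could therefore go down different treatment paths, depending on which sentence their site followed.

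**Working it through.** The plan gives no figure to reproduce. The check sets the texts side by side.

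**Triggers within the note's wording.** The permanent-stop triggers in Table 9 are:

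- Row 1: ALT above 10 x ULN for more than 4 weeks (1).
- Row 2: ALT at or above 10 x ULN for more than 4 weeks, or ALT at or above 12 x ULN recurring after a hold (2).
- Row 3: the bilirubin criterion recurring after a hold (1).
- Row 4: ALT at or above 3 x ULN with bilirubin above 2 x ULN, with new or worsening hepatitis symptoms, or with INR above 1.5 (3).

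The total is 1 + 2 + 1 + 3 = 7. The note refers to the list above without excluding any row, so on its face it reaches all seven.

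**Can the texts be reconciled?**

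1. *By the retest.* No. Section 7 puts the repeat test before withdrawal, which sets an order of steps. The permissive wording in the note applies after the retest has confirmed the criterion.
2. *By the Gilbert note.* No. It is a separate, narrow exception, and it would hardly be needed if every confirmed stop were already discretionary.
3. *By limiting the note to the monitoring and hold rows.* Possibly as intent, but not as written. The first note in the same list concerns the criteria for individual treatment discontinuation, and nothing exempts row 4.
4. *By the restart route.* No. Section 7.3 and Appendix 6 allow restart for liver events with a clear cause other than drug injury, but only after a stop. Section 7.3 itself equates meeting the stopping criteria with treatment having been discontinued.

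**Two related wording faults.** The first bullet in Section 7.1.1 points to any Table 9 condition. Read literally, it would require discontinuation in row 1, where the Monitoring Plan column only asks for closer monitoring. Appendix 6 calls for immediate withdrawal without mentioning the retest that Section 7 and the first note require.

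**Comparison with the other stopping rules.** The permanent stops in Sections 7.1.2 to 7.1.4 carry no equivalent permissive note. Section 7.1.4, for example, says "Discontinue study treatment permanently if suspect clinical sequelae of complement activation, DIVI, vasculitis or autoimmunity". The contrast is one of degree: some stops in 7.1.2 and 7.1.3 are worded as *should*, and 7.1.3 leaves further evaluation and actions to the investigator in consultation with the Medical Monitor.

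**The case against.** The best defence is that Table 9 mixes monitoring, holding and stopping. Three of its four rows begin with monitoring or a hold, so *may* suits a note covering the whole table, and a blanket *must* would contradict those rows. The specific rules then govern row 4: Appendix 6 addresses permanent discontinuation directly, and the notification step presupposes that treatment has ceased. A site would have to set aside several mandatory statements to rely on one permissive one. Safeguards also exist: the retest is evaluated before the next dose, the Medical Monitor hears within 24 hours, and possible Hy's Law events are reported as SAEs.

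Much of this stands. The surrounding text does favour a mandatory stop, and the practical risk is limited. What does not stand is that the note is harmless as drafted: it applies after confirmation, has no row restriction, and no sentence states that the mandatory text prevails.

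A reader might go further and infer that the protocol permits continued dosing in possible Hy's Law cases. Read together, the documents do not support that. A reader might also use the SAP Table 8 projections to count participants still being dosed around the amendment date. Such a count would not measure this problem, because it says nothing about how many met a liver criterion.

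**Conclusion.** The inconsistency is real and lies in a safety rule. It is a drafting fault with limited practical risk, not evidence that unsafe dosing was intended or occurred. On its face it touches seven permanent-stop triggers, three of which call for an immediate stop, and it leaves the trigger for the PegIFN bar in Section 5.3 open to two readings. The documents give no expected rate of permanent liver stops, so the number of participants affected is unknown.

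The primary analysis rules are not affected. SAP Section 4.2.1 analyses data as collected after discontinuation unrelated to wide disruptive events, and likewise for participants ineligible for PegIFN. The SAP summary of liver monitoring and stopping events (Section 4.5.3.1) would be easier to interpret if the reading applied were on record.

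The conclusion assumes that the third note means what it says, with no row restriction held in another study document.

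**What to change.** 1. Reword the third note under Table 9: *Dosing is withheld pending retest. When a criterion in the Table 9 Discontinuation column is confirmed by retest, GSK3228836 must be permanently discontinued and the Medical Monitor notified within 24 hours. Rows that call for monitoring or a hold follow the Monitoring Plan column.* Keep the Gilbert-type exception and the restart route in Section 7.3 and Appendix 6.
2. In the first bullet on required discontinuation in Section 7.1.1, refer to the Table 9 Discontinuation column instead of to any Table 9 condition.
3. Align Appendix 6: withhold dosing immediately, and make withdrawal from treatment permanent on confirmation.
4. If GSK3228836 dosing has ended, record in a clarification note which reading was applied to any participant who met a permanent-stop criterion.

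The cost is protocol wording, by amendment or clarification letter. No threshold changes, and no new visits or data are needed.
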